5.3.3. Imputation Rules for Date of Last Contact and Efficacy Assessments

5.3.3.1. Date of Last Contact

The date of last contact will be derived for patients not known to have died at the analysis cut-off using the latest complete date among the following:

- All patient assessment dates (blood draws (laboratory, PK), vital signs, performance status, ECG, tumor assessments);
- Start and end dates of anti-cancer therapies administered after study treatment discontinuation;
- AE start and end dates;

- Last date of contact collected on the ‘Survival Follow-up’ eCRF (do not use date of survival follow-up assessment unless status is ‘alive’);
- Study drug start and end dates;
- Withdrawal of consent date;
- Date of discontinuation on disposition eCRF pages (do not use if reason for discontinuation is lost to follow-up).

Only dates associated with actual examinations of the patient will be used in the derivation. Dates associated with a technical operation unrelated to patient status such as the date a blood sample was processed will not be used. Assessment dates after the cut-off date will not be applied to derive the last contact date.

5.3.3.2. Death Date

Missing or partial death dates will be imputed based on the last contact date:

- If the date is missing it will be imputed as the day after the date of last contact.
- If the day or both day and month is missing, death will be imputed to the maximum of the full (non-imputed) day after the date of last contact and the following:
 - Missing day: 1st day of the month and year of death
 - Missing day and month: January 1st of the year of death

5.3.3.3. Tumor Assessments

All investigation dates (eg, X-ray, CT scan) must be completed with day, month and year.

If there are multiple scan dates associated with an evaluation, ie, radiological assessments occur over a series of days rather than the same day, the choice of date of assessment could impact the date of progression and/or date of response. If there are multiple scan dates associated with an evaluation, the earliest of the scan dates associated with the evaluation will be used as the date of assessment.

If one or more investigation dates for an evaluation are incomplete but other investigation dates are available, the incomplete date(s) are not considered for calculation of the assessment date and assessment date is calculated as the earliest of all investigation dates (eg, X-ray, CT-scan).

If all measurement dates for an evaluation have no day recorded, the 1st of the month is used.

If the month is not completed, for any of the investigations for an evaluation, the respective assessment will be considered to be at the date which is exactly between the previous and the following assessment. If both a previous and following assessments are not available, this assessment will not be used for any calculations.

5.3.3.4. Date of Start of New Anti-cancer Therapy

Incomplete dates for start date of new anti-cancer therapy (drug therapy, non-drug locoregional therapy, radiation, surgery) will be imputed as follows and will be used for determining censoring dates for efficacy analyses and in the derivation of the end of on-treatment period. PD date below refers to PD date by investigator assessment.

- The end date of new anti-cancer therapy will be included in the imputations for start date of new anti-cancer therapy. If the end date of new anti-cancer therapy is:
 - completely missing then it will be ignored in the imputations below;
 - partially missing with only year (YYYY) available then the imputations below will consider 31DECYYYY as the end date of the new anti-cancer therapy;
 - partially missing with only month and year available then the imputations below will consider the last day of the month for MMMYYYY as the end date of the new anti-cancer therapy.
- For patients who have not discontinued study treatment at the analysis cut-off date, last dose of study treatment is set to the analysis cut-off date in the imputations below.
- If the start date of new anti-cancer therapy is completely or partially missing then the imputed start date of new anti-cancer therapy is derived as follows:

- Start date of new anti-cancer therapy is completely missing

Imputed start date = min [max(PD date + 1, last dose of study treatment + 1), end date of new anti-cancer therapy]

- Only year (YYYY) for start of anti-cancer therapy is available

IF YYYY < Year of min [max(PD date + 1, last dose of study treatment + 1), end date of new anti-cancer therapy] THEN imputed start date = 31DECYYYY;

ELSE IF YYYY = Year of min [max(PD date + 1, last dose of study treatment + 1), end date of new anti-cancer therapy];

THEN imputed start date = min [max(PD date + 1, last dose of study treatment + 1), end date of new anti-cancer therapy];

ELSE IF YYYY > Year of min [max(PD date + 1, last dose of study treatment + 1), end date of new anti-cancer therapy];

THEN imputed start date = 01JANYYYYY.

- Both Year (YYYY) and Month (MMM) for start of anti-cancer therapy are available

IF

YYYY = Year of min [max(PD date + 1, last dose of study treatment + 1), end date of new anti-cancer therapy], AND

MMM < Month of min [max(PD date + 1 day, last dose of study treatment + 1 day), end date of new anti-cancer therapy];

THEN

imputed start date = DAY (Last day of MMM) MMM YYYY;

ELSE IF

YYYY = Year of min [max(PD date + 1, last dose of study treatment + 1), end date of new anti-cancer therapy], AND

MMM = Month of min [max(PD date + 1 day, last dose of study treatment + 1 day), end date of new anti-cancer therapy];

THEN

imputed start date = min [max(PD date + 1 day, last dose of study treatment + 1 day), end date of new anti-cancer therapy];

ELSE IF

YYYY = Year of min [max(PD date + 1, last dose of study treatment + 1), end date of new anti-cancer therapy], AND

MMM > Month of min [max(PD date + 1 day, last dose of study treatment + 1 day), end date of new anti-cancer therapy];

THEN

imputed start date = 01 MMM YYYY;

ELSE IF

YYYY < Year of min [max(PD date + 1, last dose of study treatment + 1), end date of new anti-cancer therapy];

THEN

imputed start date = DAY (Last day of MMM) MMM YYYY;

ELSE IF

YYYY > Year of min [max(PD date + 1, last dose of study treatment + 1), end date of new anti-cancer therapy];

THEN

imputed start date = 01 MMM YYYY.

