8.1.4.2. Recording Non-serious AEs and SAEs on the CRF

During the active collection period, both non-serious AEs and SAEs are recorded on the CRF.

Follow-up by the investigator may be required until the event or its sequelae resolve or stabilize at a level acceptable to the investigator, and Pfizer concurs with that assessment.

If a patient begins a new anticancer therapy, the recording period for non-serious AEs ends at the time the new treatment is started; however, SAEs must continue to be recorded on the CRF during the above-indicated active collection period.

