3. ENDPOINTS AND BASELINE VARIABLES: DEFINITIONS AND CONVENTIONS

3.1. Primary Endpoints

- Adverse events (AEs) and laboratory abnormalities as graded by National Cancer Institute (NCI) Common Terminology Criteria for Adverse Events (CTCAE) v.4.03.

AEs will be graded by the investigator according to the CTCAE v.4.03 and coded using the Medical Dictionary for Regulatory Activities (MedDRA).

Laboratory abnormalities as characterized by type, severity (as graded by NCI-CTCAE v.4.03) and timing.

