5.2.5. Definition of Start of New Anti-cancer Drug Therapy

Start date of new anti-cancer drug therapy is used to determine the end of the on-treatment period (see [Section 5.2.7](#)).

The start date of new anti-cancer drug therapy is the earliest start date of anti-cancer drug therapy recorded in the 'Follow-up Cancer Therapy' eCRF pages that is after the first dose of study treatment. When start date of anti-cancer drug therapy is missing or partially missing, the imputation rules described in [Section 5.3.3.4](#) should be applied using only data from the 'Follow-up Cancer Therapy' eCRF pages.

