5.2.7. Definition of On-treatment Period

Safety endpoints will be summarized based on the on-treatment period unless otherwise specified.

On-treatment period is defined as the time from the first dose of study treatment through minimum (30 days + last dose of study treatment, start day of new anti-cancer drug therapy – 1 day).

Safety data collected outside the on-treatment period as described above will be listed and flagged in listings but not summarized.

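### An imputed start date for the next anti-cancer drug can shorten, and sometimes remove, the 30-day post-dose window in the primary safety summaries

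*SAP*

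**What the plan says.** SAP 5.3.3.4 says that the imputed start date "will be used for determining censoring dates for efficacy analyses and in the derivation of the end of on-treatment period". Three cases matter here.

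- **Start wholly missing:** "Imputed start date = min [max(PD date + 1, last dose of study treatment + 1), end date of new anti-cancer therapy". Call this value the reference date.
- **Partial date that matches:** if only the year is recorded and it equals the reference year, or if month and year both equal those of the reference date, the reference date is used again.
- **Partial date that is later:** the first day of the recorded month or year is used ("imputed start date = 01 MMM YYYY" for a month).

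SAP 5.2.5 applies these rules to drug therapy when it sets the end of the on-treatment period. Under SAP 3.5.1 and 5.2.7 that period runs from first dose "through minimum (30 days + last dose of study treatment, start day of new anti-cancer drug therapy", less one day. SAP 5.2.7 adds: "Safety data collected outside the on-treatment period as described above will be listed and flagged in listings but not summarized".

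AEs and laboratory abnormalities are the primary endpoint (SAP 3.1). Their primary analysis is SAP 6.6.1 to 6.6.5, where the treatment-emergent AE, SAE and laboratory grade tables use the on-treatment period.

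Two outputs do not depend on the new therapy. Immune-related AEs are identified through 90 days after last dose whatever the new-therapy date (SAP Appendix 1). Deaths within 30 days of last dose are tabulated without a new-therapy cut (SAP 6.6.2).

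**The concern.** A choice that is reasonable for censoring progression endpoints is reused where it works the other way. In the missing and matching cases it picks the first possible day after last dose and progression, and that is the choice that shortens the safety window most. Elsewhere the SAP leans towards inclusion: a wholly missing AE onset is set to the start of study treatment (SAP 5.3.2.2).

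The imputed date can also conflict with how the data were collected. Protocol 8.1.4 collects AEs for at least 90 days after last dose, but Protocol 8.1.4.2 says that once new anticancer therapy begins, "the recording period for non-serious AEs ends at the time the new treatment is started". A non-serious AE with onset on post-dose day 15 is therefore evidence that the new drug had not started by then. An imputed start on day 1 overrides that evidence and takes the AE out of the tables.

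At stake is under-counting in the primary safety tables of a study of about 20 patients, where one patient is 1/20 = 5 percentage points of any AE rate. A fatal AE with onset after last dose could also be missing from the table of treatment-emergent AEs leading to death while the patient is counted among deaths within 30 days.

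**Working it through.** **The plan's own figure.** SAP 5.1.1 gives at least 88% probability of seeing an AE of 10% incidence in 20 patients. 1 − 0.9^20 = 0.8784, which rounds to 88% (strictly, it is just under).

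**Rules in symbols.** L = last dose, P = date of progression, E = end date of the new therapy.

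- Reference date R = min[max(P + 1, L + 1), E]. With no P, I read the inner term as L + 1.
- Imputed start S = R if the start is wholly missing or matches R's period; S = first day of the recorded period if that is later than R's.
- On-treatment end T = min(L + 30, S − 1). Post-dose days kept = T − L.
- Loss = true window − imputed window, counted as zero if the imputed window is not the shorter.

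**Results**, assuming that E does not bind and that the new drug truly started after L:

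| Recorded start | Setting | S | Days kept of 30 | Possible loss |
|---|---|---|---|---|
| None | P on or before L, or absent | L + 1 | 0 | 0–30 |
| None | P = L + 8 | L + 9 | 8 | 0–22 |
| None | P = L + 40 | L + 41 | 30 | 0 |
| Year, same as R | L 10 Jun, P before L | 11 Jun | 0 | 0–30 |
| Next year | L 10 Dec, no P | 1 Jan | 21 | 0–9 |
| June | L 10 Jun, P before L | 11 Jun | 0 | 0–19 |
| July | L 10 Jun, P before L | 1 Jul | 20 | 0–10 |
| August | L 10 Jun, P before L | 1 Aug | 30 | 0 |
| February | L 20 Jan, P + 1 not in February or later | 1 Feb | 11 | 0–19 |

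The February row depends on P. With P on 10 Feb, R is 11 Feb, the month matches, and 21 days are kept.

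One full example: L = 1 Jun, true start 30 Jun, only June recorded, no P. The true window ends on 29 Jun (28 days). The imputed start is 2 Jun, so the imputed window is 0 days and 28 days are lost.

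**Effect on the 88%.** The inputs here are assumptions. Let k of 20 patients wrongly lose the whole window, and let a share s of a 10% AE risk fall only in it. The detection probability is 1 − 0.9^(20−k) × [1 − 0.1(1 − s)]^k:

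- k = 1, s = 0.10: 87.7%
- k = 2, s = 0.25: 87.2%
- k = 5, s = 0.50: 84.1%

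The effect is small unless many patients have incomplete dates.

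**The case against.** The best defence has four parts.

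1. **The full 30 days are not always owed.** The SAP deliberately ends the window the day before a new drug starts, so the fair comparator is the true window. This stands. In the February example, a true start of 1 Feb means nothing is lost, and 3 Feb means two days. If progression followed last dose but the drug started before it, the imputed window is too long.
2. **Much of the safety output is protected.** Immune-related AEs have their own Grade 3 or higher, serious, fatal and discontinuation tables, and 30-day deaths are counted separately. Other events are listed and flagged, and SAP 5.3.1 flags imputed values in listings. With about 20 patients in one arm and no hypothesis test, those listings are readable. This stands, but listings do not correct the primary tables.
3. **Protocol 8.1.4.2 proves less than it seems.** A reader might infer that the imputed date also contradicts the collection rules for SAEs and laboratory grades. It does not: SAEs continue to be recorded after a switch, and that section says nothing on laboratory tests. Even for non-serious AEs, the argument assumes that the site stopped recording at the right time.
4. **The alternative errs too.** It would attribute some next-line toxicity to study treatment. That is true, but it is the cautious direction for a safety endpoint, and the SAP already accepts it for immune-related AEs.

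**Conclusion.** The point holds as a gap in the rule with a cheap remedy. With a wholly missing drug start date, or one whose recorded year or month matches the reference date, the on-treatment period can end as early as the day of last dose. That happens when progression is on or before last dose or absent. The first of these is an expected pattern, since Protocol 5.4.3 allows treatment to continue while progression is being confirmed and, in some cases, afterwards. An earlier therapy end date could end the period sooner still.

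The loss is 0 to 30 days per affected patient. A table changes only if a new or worsened event, or a worse laboratory grade, falls in the wrongly removed days.

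A reader might infer that every incomplete date removes the whole window, or that a particular share of patients loses most of it. The documents support neither. A later recorded month or year often costs little or nothing, progression 30 or more days after last dose costs nothing when the date is wholly missing, and no count of incomplete dates is given. Only drug dates matter here: radiation, surgery and non-drug locoregional dates do not end the on-treatment period.

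**What to change.** Keep SAP 5.3.3.4 unchanged for efficacy censoring. In SAP 5.2.5 and 5.3.3.4, add a separate drug start date used only for the on-treatment period:

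- **Partial date:** impute the latest date compatible with the recorded parts (last day of the recorded month, or 31 December of the recorded year), but not after the therapy's end date.
- **Wholly missing date:** keep last dose plus 30 days, unless a known therapy end date is earlier.

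The SAP already uses the last day of the period when the recorded month or year precedes the reference date, so this extends an existing convention. In the examples above, last dose 10 June with June recorded would keep 19 days (start 30 June, period ends 29 June) instead of 0. Last dose 20 January with February recorded would keep 30 instead of 11. A footnote giving the number of patients whose window rests on an imputed date would show whether the choice mattered.

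The cost is about two sentences and one extra derived date, with two start dates then held for the same therapy. Some SAEs and laboratory, ECG or vital-sign values that truly followed the new drug may enter the summaries.

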6. ANALYSES AND SUMMARIES

Refer to [Section 4](#) for definitions of analysis sets and [Section 5.2](#) for general methodology.

6.1. Primary Endpoints

6.1.1. Adverse Events and Laboratory Abnormalities

6.1.1.1. Primary Analysis

Refer to [Sections 6.6.1, 6.6.2, 6.6.3, 6.6.4 and 6.6.5](#).

6.2. Secondary Endpoint(s)

6.2.1. Efficacy Endpoints

The following analyses will be based on the FAS by treatment group. Assessment of response will be made using RECIST v1.1. Tumor-related endpoints will be analyzed separately based on investigator assessment and BICR assessment.

6.2.1.1. Objective Response

Best overall response (BOR) will be assessed based on reported overall lesion responses at different evaluation time points from the first dose of study treatment until the first documentation of PD, according to the following rules. Only tumor assessments performed on or before the start date of any further anti-cancer therapies will be considered in the assessment of BOR. Clinical deterioration will not be considered as documentation of disease progression.

BOR Based on Confirmed Responses:

- CR = at least two determinations of CR at least 4 weeks apart and before first documentation of PD.
- PR = at least two determinations of PR or better (PR followed by PR or PR followed by CR) at least 4 weeks apart and before first documentation of PD (and not qualifying for a CR).
- SD (applicable only to patients with measurable disease at baseline) = at least one SD assessment (or better) ≥ 8 weeks after first dose of study treatment and before first documentation of PD (and not qualifying for CR or PR).

- Non-CR/non-PD (applicable only to patients with non-measurable disease at baseline) = at least one non-CR/non-PD assessment (or better) ≥ 8 weeks after first dose of study treatment and before first documentation of PD (and not qualifying for CR or PR).
- PD = first documentation of PD ≤ 16 weeks after first dose of study treatment (and not qualifying for CR, PR, SD or non-CR/non-PD).
- NE: all other cases.

An objective status of PR or SD cannot follow one of CR. SD can follow PR only in the rare case that tumor increases by less than 20% from the nadir, but enough that a previously documented 30% decrease from baseline no longer holds. If this occurs, the sequence PR-SD-PR is considered a confirmed PR. A sequence of PR – SD – SD – PD would be a best response of SD if the window for SD definition has been met.

Objective Response (OR) is defined as confirmed BOR of CR or PR according to RECIST v1.1.

Patients who do not have a post-baseline radiographic tumor assessment due to early progression, who receive anti-cancer therapies other than the study treatments prior to reaching a CR or PR, or who die, progress, or drop out for any reason prior to reaching a CR or PR will be counted as non-responders in the assessment of OR. Each patient will have an objective response status (0: no OR; 1: OR). OR rate (ORR) is the proportion of patients with OR in the analysis set.

ORR by treatment group will also be calculated along with the 2-sided 95% CI using the Clopper-Pearson method (exact CI for a binomial proportion as computed by default by the FREQ procedure using the EXACT option).

In addition, the frequency (number and percentage) of patients with a confirmed BOR of CR, PR, SD, non-CR/non-PD (applicable only to patients with non-measurable disease at baseline), PD and NE will be tabulated. Patients with confirmed BOR of NE will be summarized by reason for having NE status. The following reasons will be used:

- No baseline assessment;
- No post-baseline assessments due to death;
- No post-baseline assessments due to other reasons;
- All post-baseline assessments have overall response NE;
- New anti-cancer therapy started before first post-baseline assessment;
- SD of insufficient duration (< 8 weeks after first dose of study treatment);
- PD too late (> 16 weeks after first dose of study treatment).

Special and rare cases where BOR is NE due to both early SD and late PD will be classified as ‘SD too early’ (ie, SD of insufficient duration).

6.2.1.2. Tumor shrinkage from Baseline

Tumor shrinkage will be summarized as the percent change from baseline in target lesions (sum of longest diameter for non-nodal lesion and short axis for nodal lesion) per time point. It will be derived as:

- $((\text{Sum of target lesions at week XX} - \text{sum of target lesions at baseline}) / \text{sum of target lesions at baseline}) \times 100$.

The maximum reduction in target lesions from baseline will be derived across all the post-baseline assessments until documented disease progression, excluding assessments after start of subsequent anti-cancer therapy, as:

- Minimum of $((\text{sum of target lesions at week XX} - \text{sum of target lesions at baseline}) / \text{sum of target lesions at baseline}) \times 100$.

A waterfall plot of maximum percent reduction in the sum of longest diameter for non-nodal lesions and short axis for nodal lesions from baseline will be created by treatment group. These plots will display the best percentage change from baseline in the sum of the diameter of all target lesions for each patient with measurable disease at baseline and at least one post-baseline assessment.

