5.8.4. Concomitant Radiotherapy

Local radiotherapy (limited field) of isolated lesions with palliative intent is acceptable and allowed throughout the study (ie, starting from screening through end of treatment) if considered medically necessary by the treating physician. All attempts should be made to rule out disease progression in the event of increased localized pain. If palliative radiotherapy is needed to control pain, the site(s) of disease causing pain should also be present at baseline; otherwise, painful lesion(s) requiring radiotherapy will be considered as a sign of disease progression. Investigators may consult the sponsor's medical monitor prior to starting radiotherapy or prior to restarting study treatment after the end of radiotherapy.

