Disease sites must be assessed using the same technique as baseline, including consistent administration of contrast and timing of scanning. If a change needs to be made the case should be discussed with the radiologist and the Sponsor to determine if substitution is possible. If not, subsequent objective statuses are not evaluable.

Target Disease

- Complete Response (CR): Complete disappearance of all target lesions with the exception of nodal disease. All target nodes must decrease to normal size (short axis <10 mm). All target lesions must be assessed.
- Partial Response (PR): Greater than or equal to 30% decrease under baseline of the sum of diameters of all target measurable lesions. All target lesions must be assessed.
- Stable Disease (SD): Does not qualify for CR, PR or Progression. All target lesions must be assessed. Stable can follow PR only in the rare case that the sum increases by less than 20% from the nadir (smallest sum of diameters consider baseline and all assessments prior to the time point under evaluation), but enough that a previously documented 30% decrease no longer holds.
- Progressive Disease (PD): 20% increase in the sum of diameters of target measurable lesions above the smallest sum observed (over baseline if no decrease in the sum is observed during therapy), with a minimum absolute increase of 5 mm.
- Not evaluable (NE): Progression has not been documented, and
 - one or more target lesions have not been assessed or
 - assessment methods used were inconsistent with those used at baseline or
 - one or more target lesions cannot be measured accurately (e.g., poorly visible unless due to being too small to measure) or
 - one or more target lesions were excised or irradiated and have not reappeared or increased.

Non-target Disease

- CR: Disappearance of all non-target lesions and normalization of tumor marker levels (if being followed). All lymph nodes must be 'normal' in size (<10 mm short axis).
- Non-CR/Non-PD: Persistence of any non-target lesions and/or tumor marker level (if being followed) above the normal limits.
- PD: Unequivocal progression of pre-existing lesions. Generally the overall tumor burden must increase sufficiently to merit discontinuation of therapy. In the presence of SD or PR in target disease, progression due to unequivocal increase in non-target disease should be rare.
- Not evaluable (NE): Progression has not been determined and
 - one or more non-target lesion sites have not been assessed or

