5.2.6. Definition of Start of New Anti-cancer Therapy

Start date of new anti-cancer therapy (drug, non-drug locoregional, radiation, surgery) is used for censoring in efficacy analyses (see [Section 6.2.1](#)).

The start date of new anti-cancer therapy is the earliest date after the first dose of study treatment amongst the following:

- Start date of anti-cancer drug therapy recorded in the 'Follow-up Cancer Therapy' eCRF pages;

- Start date of anti-cancer non-drug locoregional therapy recorded in the eCRF pages related to the follow-up non-drug locoregional treatments;
- Start date of radiation therapy recorded in ‘Concomitant Radiation Therapy’, and ‘Follow-up Radiation Therapy’ eCRF pages with ‘Treatment Intent’ = ‘Curative in intent’;
- Surgery date recorded in ‘Concomitant Surgery’, and ‘Follow-up Surgery’ eCRF pages when ‘Surgery Outcome’ = ‘Resected’ or ‘Partially Resected’.

When start date of anti-cancer therapy is missing or partially missing, the imputation rules described in [Section 5.3.3.4](#) should be applied using ‘Follow-up Cancer Therapy’ eCRF page, eCRF pages related to the follow-up non-drug locoregional treatments, ‘Concomitant Radiation Therapy’, ‘Follow-up Radiation Therapy’, ‘Concomitant Surgery’, and ‘Follow-up Surgery’ eCRF pages.

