5.2.11. Adequate Post-baseline Tumor Assessment

An adequate post-baseline assessment is defined as an assessment where a response of CR, PR, SD, non-CR/non-PD, or PD can be determined (see [Section 6.2.1.1](#)). Time points where the response is not evaluable (NE) or no assessment was performed will not be used for determining the censoring date.

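### Best tumor shrinkage in SAP 6.2.1.2 keeps scans taken after palliative radiotherapy to a target lesion, so radiation shrinkage can show as drug effect in the waterfall plot

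*SAP*

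**What the plan says.** SAP 6.2.1.2 defines percent change in the target-lesion sum at each visit and takes the minimum as the patient's best change. On the window it says "The maximum reduction in target lesions from baseline will be derived across all the post-baseline assessments until documented disease progression", and then "excluding assessments after start of subsequent anti-cancer therapy". It lists no other exclusion. The waterfall plot shows "the best percentage change from baseline in the sum of the diameter of all target lesions", and a bar is drawn "for each patient with measurable disease at baseline and at least one post-baseline assessment"; that assessment need not be an adequate one.

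Four other places bear on this:

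- **SAP 5.2.6** defines new anti-cancer therapy for the efficacy analyses of Section 6.2.1. Radiation counts only where the recorded intent is "Curative in intent". Surgery counts where a lesion was resected or partially resected.
- **Protocol 5.8.4**: "Local radiotherapy (limited field) of isolated lesions with palliative intent is acceptable and allowed throughout the study". For pain control, the treated site should already have been present at baseline. Target lesions are not excepted.
- **Protocol Appendix 3** makes target status NE, where progression has not been documented, if "one or more target lesions were excised or irradiated and have not reappeared or increased". The same applies if a target lesion was not assessed.
- **SAP 5.2.11**: "Time points where the response is not evaluable (NE) or no assessment was performed will not be used for determining the censoring date". That rule is written for censoring; 6.2.1.2 does not take it up.

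**The concern.** A waterfall bar is read as what the study drugs did to the measured tumor. If a target lesion was irradiated, its later shrinkage may be due to the radiation. Appendix 3 recognizes this by making the time point NE, but the shrinkage rule has no matching limit. Because the summary is a minimum, any radiation effect that produces the lowest value is the one selected.

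At stake is a descriptive display. In a single-arm study of about 20 patients with no hypothesis test, such displays carry much of what readers take away about activity. A patient whose post-baseline scans are all NE could have a best overall response of NE and still show a shrinkage bar.

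**Working it through.** The plan gives no figure on this point. Its one design figure is the probability of at least one AE with 20 patients and 10% incidence: 1 - 0.9^20 = 87.8%, which rounds to the stated 88%. Only n=20 is used below.

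**Does the scan stay in?**

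1. The window in SAP 6.2.1.2 closes at documented PD or at subsequent anti-cancer therapy.
2. Palliative radiotherapy is not new anti-cancer therapy under SAP 5.2.6, so it does not close the window.
3. The irradiated site can be a target lesion, because Protocol 5.8.4 expects a painful site to have been present at baseline.
4. After irradiation, target status is NE unless the lesion has reappeared or increased, or progression is documented. NE is not PD, so the window stays open.
5. The NE rule in SAP 5.2.11 concerns the censoring date, so it does not remove the scan from the minimum.

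Read literally, the scan is NE for response but eligible as the best change.

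**How large can the effect be?** The formula in SAP 6.2.1.2 is 100 × (sum at visit - baseline sum) / baseline sum. Assume k equal target lesions (Appendix 3 allows at most 5), one irradiated and shrinking by a fraction s, the others unchanged. The change is then -100 × s / k.

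| k | s = 0.3 | s = 0.5 | s = 1.0 |
|---|---|---|---|
| 1 | -30.0% | -50.0% | -100.0% |
| 2 | -15.0% | -25.0% | -50.0% |
| 3 | -10.0% | -16.7% | -33.3% |
| 4 | -7.5% | -12.5% | -25.0% |
| 5 | -6.0% | -10.0% | -20.0% |

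For unequal lesions of 40 and 30 mm, with the smaller one halved: (40 + 15 - 70) / 70 = -21.4%.

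To reach the -30% that defines PR for target lesions, the irradiated lesion's share w of the baseline sum must satisfy w × s ≥ 0.30. That means w ≥ 0.30 for a complete radiation effect and w ≥ 0.60 for halving.

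**Direction.** For a patient who also has evaluable scans, adding visits to a minimum can only lower the value or leave it unchanged. Under the limit proposed below, the assumed patients, whose other lesions do not move, would show 0% from their evaluable scans.

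**Weight.** One patient is 1/20 = 5% of the bars. The documents give neither lesion sizes nor a radiotherapy rate, so the number affected cannot be computed.

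**The case against.** **The term may already cover palliative radiotherapy.** SAP 6.2.1.2 does not cross-refer to 5.2.6, although the TTP and PFS sections do. SAP 6.5.5, which carries the title Subsequent Anti-cancer Therapies, lists therapy from the concomitant radiation page with no intent filter. This part stands: the term is ambiguous. But 6.2.1.2 lies within the efficacy section that 5.2.6 says it serves, and the 6.5.5 tabulation of therapy after discontinuation leaves the concomitant radiation page out. The ambiguity is itself a reason for one clarifying phrase.

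**Few patients and a minor display.** The radiotherapy is limited-field, to isolated lesions. Bone disease is non-measurable under Appendix 3 unless it has a measurable soft-tissue component, so irradiated bone will often not be a target lesion. Shrinkage is not among the endpoints in Protocol Section 2 or SAP 3.2. All this stands and keeps the point minor.

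**Stronger readings that the documents do not support.**

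- A reader might infer that an unmeasured lesion is summed as zero, so that 40 + 30 mm with the second lesion missing becomes (40 - 70) / 70 = -42.9%. No section prescribes a partial sum. SAP 6.2.1.2 speaks of all target lesions, and SAP 5.3.1 rules out imputation unless otherwise specified. The SAP is silent on this case.
- A reader might infer the same problem for excised lesions. The surgery item in 5.2.6 already ends the window there, on the same reading of the term.
- A reader might infer that the response rate is inflated, or that any mismatch between waterfall and ORR is an error. ORR rests on confirmed response status, where these visits are NE. It also uses non-target and new lesions, so the two can differ by design.

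**Conclusion.** The point holds for palliative radiotherapy to a target lesion. Followed literally, SAP 6.2.1.2 lets a time point that Appendix 3 calls NE become a patient's best change, with an error toward larger shrinkage. Under the assumed sizes, halving one lesion moves the bar by 10 to 50 percentage points as the number of equal target lesions goes from five to one; with two lesions it moves by 25.

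This rests on reading *subsequent anti-cancer therapy* as the Section 5.2.6 definition, on assumed lesion sizes and radiation effects, and on an unknown frequency. ORR, DCR, DR, TTP and PFS do not change. It is a low-priority improvement that is cheap to make.

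**What to change.** In SAP 6.2.1.2:

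1. State that *subsequent anti-cancer therapy* has the meaning given in Section 5.2.6.
2. Replace the reference to all post-baseline assessments by: *all post-baseline assessments at which every target lesion was measured and the target-lesion status is not NE under Protocol Appendix 3 (including NE because a target lesion was irradiated and has not reappeared or increased)*. The waterfall condition should then require at least one such assessment.
3. In the by-visit percent change and the ADA line plot of SAP 6.2.5.3, apply the same limit or flag the affected points.

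The clause on every lesion being measured settles the case on which the SAP is silent. It is needed beside the NE clause because a visit can be PD, and so not NE, with a target lesion unmeasured. The limit follows Appendix 3 and does not drop every visit after irradiation, since a blanket exclusion would also delete visits at which the irradiated lesion grew.

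The cost is one sentence, a cross-reference and a few lost bars or points. No change to the radiotherapy rules is asked for.
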